2.6.1 Secondary endpoint(s)

The analysis of historic data from non-NAFLD patients suggested that the distribution of ALT values might be highly skewed to the left; however, after a log-transformation the distribution appeared quite symmetric, bell-shaped and could be well approximated by a normal distribution. Therefore, the log-transformed ALT-values was planned to be used for the analysis.

For this secondary objective, this study was meant as a Proof-of-Concept study, i.e. to evaluate if there is any evidence for a beneficial effect on this endpoint and to provide the basis for the planning of further, confirmatory studies; therefore a Bayesian methodology seemed adequate for the analyses of possible drug effects on ALT.

DLQI at Week 12

The DLQI measures functional disability of adult patients with dermatological disorders and had been utilized as a relevant clinical measure in a range of dermatology clinical trials. The DLQI is a simple, validated, self-administered 10-item questionnaire. The instrument contains 6 functional scales (i.e. symptoms and feeling, daily activities, leisure, work and school, personal relationships, treatment).

Each question is answered with the following response: "not at all," "a little," "a lot," or "very much". Seven scores will be derived from the DLQI: the total score of each of the six dimensions as well as the total score over all items. The higher the score, the more quality of life is impaired.

2.6.2 Statistical hypothesis, model, and method of analysis

It was planned to produce a sample from the posterior distribution of the difference between treatments of the log(ALT) levels using the BAYES-option in SAS PROC GENMOD (with the default, non-informative prior). These posterior samples were planned to be re-transformed (exponentiated) and the percentage of samples < 1, < .9, <.8 and <.7 (corresponding to the posterior probabilities of any reduction resp. reductions of at least 10%, 20% or 30% of ALT

levels under secukinumab compared to placebo) were planned to be calculated. It was specified that the study will suggest to continue the development of secukinumab for hepatic inflammation, if the posterior probability of any effect (significance) was at least 90% and if the posterior probability of a relevant effect (> 20% reduction) was at least 50%.

It was planned to derive for the total DLQI as well as for each of its 7 sub-dimensions the percentage change from baseline. Descriptive summary statistics should have been provided for absolute values as well as for the percentage change by visit and treatment group. Additionally, the percentage of patients achieving a DLQI-score of 0 or 1 (DLQI 0/1) was planned to be tabulated.

2.6.3 Handling of intercurrent events

Missing values of key secondary endpoints were not replaced. Other outcomes were not analyzed.

2.6.4 Handling of missing values not related to intercurrent event

Missing values of key secondary endpoints were not replaced. Other outcomes were not analyzed.

2.6.5 Sensitivity analyses

Not applicable.

2.6.6 Supplementary analyses

Not applicable.

2.7 Safety analyses

For all safety analyses, the Safety Set was used. All listings and tables were presented by treatment group.

Safety summaries (tables, figures) included only data from the on-treatment period with the exception of Baseline data, which were summarized where appropriate (e.g. change from Baseline summaries). In particular, summary tables for AEs summarized only on-treatment events, with a start date during the on-treatment period (i.e. treatment-emergent AEs as defined below).

2.7.1 Adverse events (AEs)

All information obtained on AEs was displayed by treatment group and patient.

The number (and percentage) of patients with treatment-emergent AEs was summarized in the following ways:

- By treatment group, primary SOC and PT.
- By treatment group, primary SOC, PT and maximum severity.

Separate summaries were provided for study medication related AEs, death, serious AEs, other significant AEs leading to discontinuation.

2.7.2 Deaths

A summary for deaths including on-treatment and post-treatment deaths was provided.

2.7.3 Laboratory data

All laboratory data were listed by treatment group, patient, and visit and if normal ranges are available abnormalities were flagged.

It was planned to provide summary statistics by treatment and visit and change from baseline.

2.7.4 Other safety data

2.7.4.1 ECG and cardiac imaging data

Not applicable.

2.7.4.2 Vital signs

All vital signs data were listed by treatment group, patient, and visit/time, and if ranges were available, abnormalities were flagged.

It was planned to perform analysis of the vital sign measurements using summary statistics for the change from Baseline for each post-Baseline visit by vital sign and treatment group.

2.8 Pharmacokinetic endpoints

Not applicable.

2.9 PD and PK/PD analyses

Not applicable.

2.12 Other Exploratory analyses

Not applicable.

2.13 Interim analysis

No interim analysis was planned.

4 Change to protocol specified analyses

Due to premature discontinuation of the study after low recruitment, the following changes were made:

- RAS and FAS population were identical, thus a separate analysis of the RAS population was omitted.
- Statistical modeling of the primary endpoint and presentation of percentages of patients reaching PASI90 was omitted. Only the course of PASI was presented.
- No imputation for missing values was performed. All data was analyzed as observed.
- The sensitivity analysis for the primary objective was omitted.
- Bayes analyses of the key secondary objective was omitted. Only sample statistics for ALT were presented. No log-transformation of ALT values was performed.
- DLQI data was only listed by treatment group, patient and visit.
- Summary statistics for laboratory values were omitted.
- Sample statistics for vital signs by visit and change from baseline were omitted.

5 Appendix

Not applicable, as no additional information is necessary.

6 Reference

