The purpose of this Statistical Analysis Plan (SAP) is to describe all analyses necessary for the final clinical study report (CSR). The SAP is based on final study protocol version 01 (Amendment 1) dated 05-Jun-2020. As the study was discontinued prematurely, only an abbreviated analysis will be performed.

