1.2 Study objectives, endpoints and estimands

The following tables shows the objectives and endpoints as specified in the study protocol.

[figure not shown]
Table 1 Objectives and related endpoints

[figure not shown]
Objectives	Endpoints	
Primary objectives	Endpoints for primary objectives	
To demonstrate superiority of secukinumab compared to placebo in patients with moderate to severe chronic plaque-type psoriasis and NAFLD with respect to PASI90 response at Week 12.	 Proportion of patients achieving PASI90 response at Week 12. 	
Secondary objectives	Endpoints for secondary objectives	

Objectives

Endpoints

- To evaluate the effect of secukinumab compared to placebo on hepatic inflammation in patients with moderate to severe psoriasis and NAFLD with respect to serum ALT levels at Week 12.
- Serum ALT level at Week 12.
- To evaluate the effect of secukinumab compared to placebo on quality of life in patients with moderate to severe psorials and NAFLD with respect to
- Proportion of patients achieving DLQI 0/1 at Week 12.

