2.5 Analysis supporting primary objective(s)

2.5.1 Primary endpoint(s)

The primary aim of this study was to demonstrate the superiority of secukinumab compared to placebo in patients with moderate to severe chronic plaque-type psoriasis and NAFLD with respect to PASI90 response at Week 12.

The primary endpoint variable was the PASI90 response at Week 12.

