2.5.2 Statistical hypothesis, model, and method of analysis

The null hypothesis to be rejected was that the OR of a PASI90 response for patients with secukinumab vs. patients with placebo were ≥ 1 after 12 weeks.

Let p_j denote the probability of a PASI90 response at 12 weeks for treatment group j, j=0,1 where

- 0 corresponds to placebo
- 1 corresponds to secukinumab 300 mg

The following hypotheses were tested:

$$H_0$$
: $(p_0 / 1-p_0)) / (p_1 / 1-p_1)) \ge 1$ versus H_A : $(p_0 / 1-p_0)) / (p_1 / 1-p_1)) < 1$

The primary analysis was planned to be performed comparing treatments with respect to the primary efficacy variable in a logistic regression model with the factors treatment group and center as factors and PASI score at Baseline (Day 1) as covariates. It was planned to present the OR and its 95% confidence interval (CI) and p-value. The primary analysis was based on the FAS and was planned to be performed when all patients had completed the Week 12 assessment.

As the number of patients was small when the study was discontinued only change in PASI was presented.

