2.5.6 Supplementary analyses

Not applicable.

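### The abbreviated SAP openly drops the PASI90 percentages along with the logistic model, so the report as written states no responder result for its primary endpoint

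*SAP*

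**What the plan says.** SAP Table 1 (Section 1.2) gives the endpoint for the primary objective as "Proportion of patients achieving PASI90 response at Week 12", and Section 2.5.1 confirms it: "The primary endpoint variable was the PASI90 response at Week 12". The protocol says the same in Table 2-1 and Section 12.4.1. Protocol Section 8.3.1 defines a PASI90 responder patient by patient, as a reduction of at least 90% from that patient's own baseline score.

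The planned analysis was a logistic regression giving an odds ratio, a 95% CI and a p-value (Protocol 12.4.2; SAP 2.5.2). The SAP was written after the study had stopped, and it declares its reduced scope at the start: "As the study was discontinued prematurely, only an abbreviated analysis will be performed". For the primary endpoint, Section 2.5.2 says: "As the number of patients was small when the study was discontinued only change in PASI was presented". Section 4, which lists the changes to the protocol-specified analyses, says: "Statistical modeling of the primary endpoint and presentation of percentages of patients reaching PASI90 was omitted", and leaves only the course of PASI. The same list removes the sensitivity analysis for the primary objective and adds: "No imputation for missing values was performed. All data was analyzed as observed". Section 2.5.6 provides no supplementary analysis.

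**The concern.** Section 4 removes two different things in one sentence. One is a model, which needs enough patients to be fitted and interpreted. The other is a percentage, which needs only a numerator and a denominator. The stated reason, few patients, supports the first cut but not the second.

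If the report is produced exactly as the SAP describes, it need not say how many randomized patients in each arm met the primary endpoint, or how many had a Week 12 PASI from which that could be judged. Disposition (SAP 2.3.1) covers patients included, screening failures, patients randomized and patients completing the study. Completing a 24-week study is not the same as having a Week 12 PASI. Anyone who later wants the responder data, for example to pool them with other studies, could not rely on finding them in the report.

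**Working it through.** The documents give no figure to reproduce: the visible text has no final sample size and no Week 12 counts. The check is therefore mainly a comparison of sections, followed by labelled illustrations.

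**1. What is cut and what is kept for each efficacy endpoint (SAP Section 4, with 2.5.2 and 2.7.3)**

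| Endpoint | Cut | Kept | Per-patient listing stated? |
|---|---|---|---|
| PASI90 at Week 12 (primary) | model, percentages, sensitivity analysis | course of, or change in, PASI | no |
| ALT at Week 12 | Bayesian analysis, log-transformation | sample statistics for ALT | yes, with the laboratory data (2.7.3) |
| DLQI 0/1 at Week 12 | percentage table | listing | yes |

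For ALT the SAP says "Only sample statistics for ALT were presented", so ALT is still summarized on its own scale. DLQI 0/1 loses its percentage, but a reader can count it from the listing. For PASI90 neither a summary nor a listing is stated.

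**2. Does the small sample prevent a count?** No. In the same sample the SAP keeps counts and percentages for baseline data (2.3.2) and for adverse events (2.7.1).

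**3. Does other SAP text restore the endpoint?** No. Section 2.5.2 says in the past tense that the hypotheses were tested, and 2.5.3 says that all FAS patients will be included in the PASI90 analysis. Section 4 overrides both.

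**4. Can the count be recovered from the PASI summary?** That depends on the format, which the SAP does not specify for PASI.

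*If only means were shown (assumed).* Take 10 patients, all with baseline PASI 20.
- Case A: all fall to 4.0. Mean = 4.0; improvement = (20 − 4)/20 = 80% in each patient; PASI90 = 0/10.
- Case B: eight fall to 2.0 and two to 12.0. Mean = (8 × 2.0 + 2 × 12.0)/10 = 4.0. Improvements are 90% and 40%, mean (8 × 90 + 2 × 40)/10 = 80%; PASI90 = 8/10.

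In general, at a mean improvement of 80% with individual values between 0 and 100%, the minimum is 0 responders and the maximum is the largest k with 90k ≤ 80n. For n = 4, 320/90 = 3.6, so 3. For n = 6, 480/90 = 5.3, so 5. For n = 10, 800/90 = 8.9, so 8.

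*If median and range were also shown (assumed).* The two cases separate. Case A has median 4.0 and range 4.0 to 4.0; case B has median 2.0 and range 2.0 to 12.0. With the common baseline of 20, A shows no responders and B shows at least half.

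*If absolute change were shown and baselines differ.* A fall of 18 points from 20 is 18/20 = 90%, a response. The same fall from any baseline above 20 is below 90%, so it is not. Summaries of absolute change therefore need not settle the count.

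**5. How precise would a count be?** Exact (Clopper-Pearson) 95% limits: lower = Beta quantile 0.025 with parameters (x, n − x + 1); upper = Beta quantile 0.975 with parameters (x + 1, n − x). All counts are assumed, with half responding.

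| x/n | 95% CI |
|---|---|
| 1/2 | 1.3 to 98.7% |
| 2/4 | 6.8 to 93.2% |
| 5/10 | 18.7 to 81.3% |
| 10/20 | 27.2 to 72.8% |

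**6. Effect of the missing-value rule (assumed).** If 5 of 10 observed patients respond, x/n = 50%. If the arm has 20 randomized patients and the other 10 have no Week 12 PASI, the protocol's non-response rule gives x/N = 5/20 = 25%. Termination by the sponsor could produce such a gap without any lack of drug effect.

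**The case against.** The best defence is that this is a declared and reasoned choice. The SAP announces an abbreviated analysis, gives small numbers as the reason, and lists the change where a reader would look. How much to tabulate from a study that stopped early is partly a matter of preference, and intervals as wide as those above inform little. This stands as far as it goes. It rules out any reading that the change was concealed, or that an unfavourable result was hidden behind another outcome; nothing in the documents supports either inference.

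Three narrower objections also stand:

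- A reader might infer that the primary endpoint has been replaced by something unrelated. It has not. Section 2.5.2 keeps change in PASI, which is the quantity PASI90 dichotomises.
- A reader might infer that only the primary endpoint was cut. The percentage for DLQI 0/1 went as well. The difference is that DLQI remains available in a listing, and no such listing is stated for PASI.
- A reader might infer from the 0/10 versus 8/10 example that the report could mislead to that extent. The example holds only if means alone are shown. The format the SAP states for continuous baseline and exposure data (2.3.2, 2.4.1) includes the median and range, which separate the two cases. Those sections do not say that this format applies to PASI.

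What does not stand is the step from few patients to no count. Disclosure explains the omission but does not supply the result, and imprecision argues against a test rather than against x/n.

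**Conclusion.** The point holds as a gap in descriptive reporting. As written, the abbreviated report states no PASI90 result for its primary endpoint, and the reason given covers the model, odds ratio, p-value and sensitivity analysis but not the count. No confirmatory conclusion depends on it and no effect size is claimed. The change is worth making because it is cheap and lets the report answer its own primary question descriptively.

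It would go too far to say that responders cannot be identified at all. The SAP is silent on how PASI is displayed, and a per-patient display would allow a count. The conclusion rests on the visible text, in which no section restores a PASI90 count or states a PASI listing. It also assumes that at least some patients had a Week 12 PASI, which the documents do not show. If an arm had none, the table would say so, and that too is worth reporting.

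**What to change.** In SAP Section 4 and Section 2.5.2, replace the omission of the PASI90 percentages with two outputs:

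1. A descriptive FAS table by randomized arm with the number randomized, the number with a Week 12 PASI, and observed PASI90 responders as x/n. No test. Count the Week 12 values after applying the rule in Section 2.1.1 that moves early end-of-treatment data to the nearest planned visit. This is consistent with the as-observed rule in Section 4.
2. A listing of PASI and percent change from baseline by patient and visit, as is already done for DLQI.

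An exact confidence interval is optional. So is x/N under the protocol's rule that a missing assessment counts as non-response (Protocol 12.4.3; SAP 2.5.3). If x/N is shown, label it as the originally planned rule, state that early termination affects it, and place it beside the observed figure, because it departs from the as-observed approach.

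The cost is one table, one listing and a few lines of SAP text. No new data are needed: Protocol Table 8-1 schedules PASI at baseline and Week 12. The downside is that the figures will be very imprecise and must be presented as description only.
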